10.10 Amendments to the Protocol

Should amendments to the protocol be required, the amendments will be originated and documented by the Principal Investigator. It should also be noted that when an amendment to the protocol substantially alters the study design or the potential risk to the patient, a revised consent form might be required.

The written amendment, and if required the amended consent form, must be sent to the UCSD IRB for approval prior to implementation.

10.11 Record Retention

Study documentation includes all Case Report Forms, data correction forms or queries, source documents, Sponsor-Investigator correspondence, monitoring logs/letters, and regulatory documents (e.g., protocol and amendments, IRB correspondence and approval, signed patient consent forms).

Source documents include all recordings of observations or notations of clinical activities and all reports and records necessary for the evaluation and reconstruction of the clinical research study.

Government agency regulations and directives require that the study investigator must retain all study documentation pertaining to the conduct of a clinical trial. In the case of a study with a drug seeking regulatory approval and marketing, these documents shall be retained for at least two years after the last approval of marketing application in an International Conference on Harmonization (ICH) region. In all other cases, study documents should be kept on file until three years after the completion and final study report of this investigational study.

10.12 Obligations of Investigators

The Principal Investigator is responsible for the conduct of the clinical trial at the site in accordance with Title 21 of the Code of Federal Regulations and/or the Declaration of Helsinki. The Principal Investigator is responsible for personally overseeing the treatment of all study patients. The Principal Investigator must assure that all study site personnel, including sub-investigators and other study staff members, adhere to the study protocol and all FDA/GCP/NCI regulations and guidelines regarding clinical trials both during and after study completion.

The Principal Investigator at each institution or site will be responsible for assuring that all the required data will be collected and entered onto the Case Report Forms. Periodically, monitoring visits will be conducted and the Principal Investigator will provide access to his/her original records to permit verification of proper entry of data. At the completion of the study, all case report forms will be reviewed by the Principal Investigator and will require his/her final signature to verify the accuracy of the data.

10.13 Data Reporting

The study findings will be disseminated as a prospective case series wherein related participant medical history will be reported. The degree and length of the medical history reporting will vary by participant. At the PI's discretion, only events and factors significant to the present study that are fully de-identified will be included in the dissemination of findings. Historic factors related to individual participant pain will be considered and can include past pain medication and radiation experience, or any diagnosis that contributes to radiation therapy pain.

12.0 APPENDICES

Appendix A: ECOG Performance Status Scale

ECOG Performance Status Scale	
Grade	Descriptions
0	Normal activity. Fully active, able to carry on all pre-disease performance without restriction.
1	Symptoms, but ambulatory. Restricted in physically strenuous activity, but ambulatory and able to carry out work of a light or sedentary nature (e.g., light housework, office work).

2	In bed < 50% of the time. Ambulatory and capable of all self-care, but unable to carry out any work activities. Up and about more than 50% of waking hours.
3	In bed > 50% of the time. Capable of only limited self-care, confined to bed or chair more than 50% of waking hours
4	100% bedridden. Completely disabled. Cannot carry on any self-care. Totally confined to bed or chair
5	Dead.

Appendix B. Strong and Moderate CYP3A4 Inhibitors

Strong CYP3A4 inhibitors allowed during study and include but are not limited to the following:

[figure not shown]
- Boceprevir
- Clarithromycin
- Conivaptan
- Grapefruit juice
- Indinavir
- Itraconazole
- Ketoconazole
- Lopinavir/ritonavir
- Mibefradil
- Nefazodone
- Nelfinavir
- Posaconazole
- Ritonavir,
- Saquinavir
- Telaprevir
- Telithromycin
- Voriconazole

Moderate CYP3A4 inhibitors are allowed during study and include but are not limited to the following:

- Amprenavir
- Aprepitant,
- Atazanavir,
- Ciprofloxacin,
- Darunavir/ritonavir,
- Diltiazem,
- Erythromycin,
- Fluconazole,
- Fosamprenavir,
- Grapefruit juice,
- Imatinib,
- Verapamil

Please refer to the U.S. Food and Drug Administration website, *Drug Development and Drug Interactions: Table of Substrates, Inhibitors and Inducers*, for additional information:
<http://www.fda.gov/Drugs/DevelopmentApprovalProcess/DevelopmentResources/DrugInteractionsLabeling/ucm093664.htm>

Appendix C. Numerical Rating Score (NRS) for Pain

[figure not shown]
Appendix D. Brief Pain Inventory-short form (BPI-sf)

Brief Pain Inventory (Short Form)

1. Throughout our lives, most of us have had pain from time to time (such as minor headaches, sprains, and toothaches). Have you had pain other than these everyday kinds of pain today?

Yes No

2. On the diagram, shade in the areas where you feel pain. Put an X on the area that hurts the most.

3. Please rate your pain by marking the box beside the number that best describes your pain at its **worst** in the last 24 hours.

0 1 2 3 4 5 6 7 8 9 10
No Pain Pain As Bad As You Can Imagine

4. Please rate your pain by marking the box beside the number that best describes your pain at its **least** in the last 24 hours.

0 1 2 3 4 5 6 7 8 9 10
No Pain Pain As Bad As You Can Imagine

5. Please rate your pain by marking the box beside the number that best describes your pain on the **average**.

0 1 2 3 4 5 6 7 8 9 10
No Pain Pain As Bad As You Can Imagine

6. Please rate your pain by marking the box beside the number that tells how much pain you have **right now**.

0 1 2 3 4 5 6 7 8 9 10
No Pain Pain As Bad As You Can Imagine

7. What treatments or medications are you receiving for your pain?

8. In the last 24 hours, how much relief have pain treatments or medications provided? Please mark the box below the percentage that most shows how much relief you have received.

0%	10%	20%	30%	40%	50%	60%	70%	80%	90%	100%
										
No Relief										Complete Relief

9. Mark the box beside the number that describes how, during the past 24 hours, pain has interfered with your:

A. General Activity

 0	 1	 2	 3	 4	 5	 6	 7	 8	 9	 10
Does Not Interfere										Completely Interferes

B. Mood

 0	 1	 2	 3	 4	 5	 6	 7	 8	 9	 10
Does Not Interfere										Completely Interferes

C. Walking ability

 0	 1	 2	 3	 4	 5	 6	 7	 8	 9	 10
Does Not Interfere										Completely Interferes

D. Normal Work (includes both work outside the home and housework)

 0	 1	 2	 3	 4	 5	 6	 7	 8	 9	 10
Does Not Interfere										Completely Interferes

E. Relations with other people

 0	 1	 2	 3	 4	 5	 6	 7	 8	 9	 10
Does Not Interfere										Completely Interferes

F. Sleep

 0	 1	 2	 3	 4	 5	 6	 7	 8	 9	 10
Does Not Interfere										Completely Interferes

G. Enjoyment of life

 0	 1	 2	 3	 4	 5	 6	 7	 8	 9	 10
Does Not Interfere										Completely Interferes

Appendix E. Medication Use Diary

Medication Use Diary

Protocol No.	Participant No.	Participant Initials
UCSD XXXXXX		

Instructions for completion:

- Please remember to complete this diary *daily* while participating in this study.
- Record each medication you are taking at home on a separate line. For each medication recorded, please list the date or dates that it was taken, how many times it is taken each day, the dose each time it is taken, and the reason why you are taking the medication.
- If there is any information that you do not know, please write "UNK" in the space provided.

Name of Medication	Date(s) Medication Taken (mm/dd/yy)	No. of times taken each day	Dose (each time it is taken)	Reason for Taking Medication

Please sign when the diary when all spaces are full and return to the study coordinator during your next clinic visit.

Participant Signature: _____ **Date:** _____

version dated 29DEC16

Appendix F. Laxation Diary

Laxation Diary

Protocol No.	Participant No.	Participant Initials
UCSD XXXXXX		

Instructions for completion:

- Please remember to complete this diary **daily** while participating in this study.
- Record time of each bowel movement that you have throughout the day on a separate line, and circle "am" or "pm".
- At the end of each day, please record the total number of bowel movements for that day in the space provided.
- If you did not have any bowel movement throughout the day, please leave all spaces for time blank, and record "0" in the space for total number of bowel movements.

Date								
Time (hh:mm)	am							
	pm							
Time (hh:mm)	am							
	pm							
Time (hh:mm)	am							
	pm							
Time (hh:mm)	am							
	pm							
Time (hh:mm)	am							
	pm							
Time (hh:mm)	am							
	pm							
Total # bowel movements								

Please sign when the diary has been completed at the end of the study return to the study coordinator during your next clinic visit.

Participant Signature: _____ Date: _____

version dated 29DEC16

Appendix G. Nausea/Vomiting Diary

Nausea and Vomiting Diary

Protocol No.	Participant No.	Participant Initials
UCSD XXXXXX		

Instructions for completion:

- Please remember to complete this diary **daily** while participating in this study.
- Record each episode of nausea, retching, vomiting or dry heaves that you have throughout the day on a separate line. For each episode recorded, please record the time of the episode and whether rescue medication was taken.
- At the end of each day, please record the total number of episodes for that day in the space provided.
- If you did not have any nausea, retching, vomiting or dry heaves throughout the day, please leave all spaces for type and time of episode and rescue medication blank, and record "0" in the space for total episodes.

Type of episode (nausea, retching, vomiting, dry heaves)	Time of Episode	Rescue Medication Taken (yes/no)? If yes, record on the Medication Use Diary
	am	
	pm	
	am	
	pm	
	am	
	pm	
	am	
	pm	
	am	
	pm	
	am	
	pm	
Total number of episodes in the last 24 hours? _____		

Please sign when the diary has been completed at the end of each day and return to the study coordinator during your next clinic visit.

Participant Signature: _____ Date: _____

version dated 29DEC16

Appendix H. Study Drug Diary

Study Drug Diary

Protocol No.	Participant No.	Participant Initials
UCSD XXXXXX		

Instructions for completion:

- Please complete this diary on ***each day that you take your Lazanda dose***. Enter the date and time you take Lazanda in the appropriate box. Circle "am" or "pm" next to the time for each dose.
- Please indicate the dose of Lazanda administered on each day: 1 spray in 1 nostril = 100 mcg, 1 spray in each nostril = 200 mcg, 2 sprays in each nostril = 400 mcg
- If you forget to take your dose of Lazanda before your daily radiation treatment, skip the dose for that day and resume taking Lazanda at your next scheduled radiation therapy visit. Please mark a line through the date and time for any day where a dose was missed.

Date (mm/dd/yy)	Time (hh:mm)	Dose (mcg)
	am	
	pm	
	am	
	pm	
	am	
	pm	
	am	
	pm	
	am	
	pm	
	am	
	pm	

Date (mm/dd/yy)	Time (hh:mm)	Dose (mcg)
	am	
	pm	
	am	
	pm	
	am	
	pm	
	am	
	pm	
	am	
	pm	
	am	
	pm	

Please sign when the diary has been completed at the end of the study and return to the study coordinator during your next clinic visit.

Participant Signature: _____ Date: _____

version dated 29DEC2016

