4.2.1 Radiation Simulation Visit(s)

To determine an individual patient's effective and tolerable Lazanda dose, each subject will undergo dose titration during the radiation simulation visit. Lazanda dose for all subjects on study, including those switching from another fentanyl product, will be determined according to the following procedures:

- 15 minutes prior (T-15) to beginning the radiation therapy simulation, subjects will receive an initial dose of 100 mcg (1 spray) of Lazanda in one nostril prior to lying on the CT simulation hard surface.
- If adequate analgesia is obtained within 30 minutes of administration of the 100-mcg single spray, subsequent pain episodes will be treated with this dose.
- If the subject does not experience relief after 30 minutes, he or she may take another 100 mcg in the opposite nostril **but must wait at least 2 hours** (i.e., T-15 + 2 hours) from the first spray before administering this second 100 mcg dose. The subject may delay or reschedule the simulation (within a 14 days period) or radiation delivery to achieve the adequate pain control dose.
- If adequate analgesia is still not achieved, the subject will continue to dose escalate in a step-wise manner at a minimum of 2 hours between each subsequent escalation until adequate analgesia with tolerable side effects is achieved. A maximum of 4 doses or 400 mcg allowed per day.
- Dose titration steps are further detailed in **Table 1**.

Table 1: Lazanda Dose Titration Steps

Lazanda Dose	Using
100 mcg	1 x 100 mcg spray
200 mcg	2 x 100 mcg spray (1 in each nostril)
400 mcg	4 x 100 mcg spray (2 in each nostril, alternate nostrils) or 1 x 400 mcg spray

Each bottle contains a total of 8 sprays. Lazanda bottles come in 100 mcg or 400 mcg dose. If using dose of 100 mcg with the 100-mcg spray, the patient would have total of 8 doses in a single bottle. If using dose of 200 mcg with the 100-mcg spray, the patient would have total of 4 doses in a single bottle. If using dose of 400 mcg with the 100-mcg spray, the patient would have total of 2 doses in a single bottle. Alternately, if using a bottle of the 400-mcg spray at a dose of 400 mcg, the patient would have total of 8 doses in a single bottle.

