Lazanda titration should be done with caution in patients with chronic obstructive pulmonary disease or preexisting medical conditions predisposing them to respiratory depression and in patients susceptible to intracranial effects of CO₂ retention. Caution should also be used in patients on central nervous system (CNS) depressants and potent CYP3A4 inhibitors.

The minimal effective intranasal dose from the radiation therapy simulation will be the dose used as pre-medication prior to any further radiation therapy fractions (up to 10 fractions). Lazanda should be administered 15 (T-15) minutes prior to laying on the hard surface for each simulation visit. If the response to the titrated Lazanda dose markedly changes, an adjustment of dose may be necessary to ensure that an appropriate dose is maintained as deemed by the investigator.

Subjects will be instructed on the proper use of Lazanda as follows:

- 1) Prime the device before use by spraying into the pouch (4 sprays in total). If study drug has not been used for 5 days, re-prime by spraying once.
- 2) Insert the nozzle of the Lazanda bottle a short distance (about ½ inch) into the nose and point towards the bridge of the nose, tilting the bottle slightly.
- 3) Press down firmly on the finger grips until hearing a “click” and the number in the counting window advances by one.

Subjects will also be advised that the fine mist spray is not always felt on the nasal mucous membrane and to rely on the audible click and advancement of the dose counter to confirm a spray have been administered.

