4.2.2 Radiation Treatment Visits

Lazanda will be self-administered by the subject while attending their visit to the radiation treatment center, and will be monitored closely by the clinic staff and study coordinator. Therefore, the chance for a missed dose is rare. However, should a subject miss a Lazanda dose prior to treatment fraction, he or she will be instructed to take the dose as soon as it is remembered on the same day prior to radiation.

The dose used as pre-medication prior to any radiation therapy fractions is as described in the titration schema listed above in section 4.2.1 and described in Table 1.

If a patient takes less than the minimal effective dose of Lazanda, they should be monitored closely for evidence of opioid withdrawal symptoms and reversal of central analgesic effects. In cases of known or suspected overdose, symptomatic treatment as well as monitoring of vital functions will be performed. In cases of severe intoxication, intensive care procedures will be completed. Close medical supervision and monitoring will be continued until the patient recovers.

Subjects will be required to record each self-administered dose of Lazanda on a Study Drug Diary (**Appendix H**) from the time of the radiation simulation visit through the end of radiation therapy. Details of Lazanda administration, including date and time of administration as well as number of sprays administered and total daily dose will be recorded by the subject on the Study Drug Diary.

Lazanda will be dispensed to the patient in nasal spray bottle format, within a child-resistant outer container. The child-resistant container should be opened just prior to initial product use. Subjects will be instructed to replace the bottle in the child-resistant container and out of reach of children between doses. Subjects will also be instructed to avoid consumption of grapefruit or grapefruit juice as this is a potent inhibitor of the CYP3A4 enzyme.

There are additional no requirements for monitoring of vital signs or other parameters following Lazanda administration. Treatment with Lazanda does not require that any pre-treatment parameters be met prior to dispensing and/or administration. However, subjects will be advised not to drive during study participation and must be accompanied to all treatments.

Any adverse events or serious adverse events resulting from known or suspected overdose will be reported according to instructions in **Section 7.6** of the protocol.

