5.1.11.6 Study Drug Diary

Patients will complete a daily study drug diary (**Appendix H**) during the time that they are receiving Lazanda. Participants will be asked to complete this diary even on days when a Lazanda dose was missed or not taken. Details of Lazanda administration, including date and time of administration as well as number of sprays administered and total daily dose will be recorded. The study drug diary will be reviewed with the patient during each visit to clinic or the radiation treatment center, and a copy will be collected by a member of the study team. This diary will be used in combination with returned nasal spray bottles to support drug accountability.

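### The Study Drug Diary's dose key fits only the 100-mcg bottle: followed literally, it records a correct single 400-mcg spray as 100 mcg

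*Combined protocol and SAP*

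**What the plan says.** The titration table in Section 4.2.1 lists doses of 100, 200 and 400 mcg and gives two ways to deliver the highest: "4 x 100 mcg spray (2 in each nostril, alternate nostrils) or 1 x 400 mcg spray". The text below the table confirms that one spray from the stronger bottle is a full dose: "if using a bottle of the 400-mcg spray at a dose of 400 mcg, the patient would have total of 8 doses".

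Section 8.1 issues one 100-mcg bottle at simulation for titration. From the first radiation visit the investigator may supply 100-mcg bottles, 400-mcg bottles or both. On the dose itself, Section 4.2.1 says: "The minimal effective intranasal dose from the radiation therapy simulation will be the dose used as pre-medication". It also allows later change: "If the response to the titrated Lazanda dose markedly changes, an adjustment of dose may be necessary".

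For the record, Section 4.2.2 says that the "number of sprays administered and total daily dose will be recorded by the subject on the Study Drug Diary", and Section 5.1.11.6 repeats this. The form in Appendix H asks for the dose given each day and supplies one key: "1 spray in 1 nostril = 100 mcg, 1 spray in each nostril = 200 mcg, 2 sprays in each nostril = 400 mcg". Its columns are date, time and dose in mcg. There is no column for bottle strength or number of sprays.

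**The concern.** The key treats the spray count as if it fixed the dose, but the dose also depends on the bottle. For one regimen that the protocol permits, following the printed instruction gives a wrong entry. Section 5.1.11 has patients complete diaries without help from the study team, so the key is the only conversion in front of them when they write.

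The 400-mcg bottle is a realistic choice for a subject at the top dose. By Section 4.2.1, a 100-mcg bottle holds 2 doses of 400 mcg and a 400-mcg bottle holds 8. Ten fractions at 400 mcg need 10 / 2 = 5 of the weaker bottles, or 10 / 8 = 1.25, so 2, of the stronger.

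At stake is the accuracy of a dose record for a Schedule II opioid. Section 5.1.11.6 gives the diary a formal role: "This diary will be used in combination with returned nasal spray bottles to support drug accountability". Separately, the form does not capture the spray count that the protocol says it captures.

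**Working it through.** **Inputs.** Key: 1 spray = 100 mcg, 2 sprays = 200 mcg, 4 sprays = 400 mcg (Appendix H). Strengths: 100 or 400 mcg per spray (Section 8.1). Permitted regimens: 1, 2 or 4 sprays of 100 mcg, or 1 spray of 400 mcg (Section 4.2.1).

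**Formula.** Dose given = number of sprays × mcg per spray.

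**Step 1: reproduce the key.** With the 100-mcg bottle, 1 × 100 = 100, 2 × 100 = 200 and 4 × 100 = 400. All three lines are correct.

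**Step 2: pass each permitted regimen through the key.**

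| Regimen | Dose given (mcg) | Entry by the key (mcg) |
|---|---|---|
| 1 spray, 100-mcg bottle | 100 | 100 |
| 2 sprays, 100-mcg bottle | 200 | 200 |
| 4 sprays, 100-mcg bottle | 400 | 400 |
| 1 spray, 400-mcg bottle | 400 | 100 |

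In the last row the entry is low by 400 − 100 = 300 mcg, a factor of 400 / 100 = 4.

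**Step 3: invert the table.** An entry of 100 corresponds to a true dose of 100 or 400 mcg. An entry of 200 means 200 mcg only, and an entry of 400 means 400 mcg only. The ambiguity lies in one of the three possible entries.

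**Step 4: would the sequence of entries reveal the error?**

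- *Titrated to 400 mcg at simulation, then given the 400-mcg bottle.* Titration uses the 100-mcg bottle, where the key is correct, so a 400 entry already exists. The keyed record then falls from 400 to 100 with no prescribed reduction. This is visible.
- *Raised step by step during radiation, 100 to 200 to 400 mcg by one spray.* The keyed record reads 100, 200, 100. It shows a halving where the dose doubled. This is visible.
- *Raised directly from 100 mcg to one 400-mcg spray during radiation.* The keyed record reads 100, 100. The diary shows no change. The NRS log (Appendix I) does not help here, because its fraction rows carry no dose.

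**Step 5: compare the protocol with the form.** Sections 4.2.2 and 5.1.11.6 say the number of sprays is recorded, and Appendix H has no place for it. This mismatch exists whichever bottle is used.

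**The case against.** The strongest reply is that the wrong entry is possible but not automatic, and that much else in the protocol would expose it. The column asks for micrograms, so a subject who knows the dose is 400 mcg may simply write 400. Section 4.2.2 has dosing at the radiation centre, where it "will be monitored closely by the clinic staff and study coordinator". Section 5.1.11.6 has the diary reviewed at each visit and read with the returned bottles. Section 8.1 ties both initial supply and refills to the investigator's dose decision, so a 400-mcg bottle reaches a subject only through a known prescription. Section 8.1.2 keeps separate records of dosages. All of this stands and keeps the point minor. None of it makes the key correct or supplies the missing field.

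Four stronger readings are tempting, and the documents do not support them:

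- *That diary entries in general fail to identify the dose.* Only an entry of 100 is ambiguous among the permitted regimens.
- *That the error is invisible for anyone first raised to 400 mcg during radiation.* It is hidden only by a direct move from 100 to 400 mcg. Section 4.2.1 escalates step by step through 200 mcg, Section 4.1 carries titration through the end of radiation, and Section 4.2.2 ties fraction doses to that schema. The adjustment clause leaves changes to the investigator, so a direct jump is not strictly excluded, but it skips a listed step.
- *That spray-count reconciliation would pass the wrong record, or that a large cumulative shortfall would build up.* No section describes matching counts without regard to bottle strength. A total of 10 × 300 = 3,000 mcg over ten fractions requires the same wrong entry every time, uncorrected despite review at each visit.
- *That the key could lead a subject to take 4 × 400 = 1,600 mcg.* It is worded as a recording instruction, dosing is monitored, and Section 4.2.1 caps the titration day at 400 mcg.

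**Conclusion.** The point holds as a minor error in the form. The key is correct for the 100-mcg bottle and wrong for the one permitted regimen that uses the 400-mcg bottle, where a keyed entry is four-fold low (300 mcg per entry). The form also omits the spray count that two sections say it holds.

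The consequence is limited to dose-record and accountability accuracy for subjects who use a 400-mcg bottle and follow the key. The documents do not say how many that will be. With about six subjects planned (Section 9.2) it may be none, and subjects using only 100-mcg bottles are unaffected by the key error.

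A reader might infer that efficacy results are at risk. Sections 9.3.1 to 9.3.4 name no Lazanda dose term in any model, so no planned efficacy estimate changes. This takes the exploratory 24-hour opioid covariate to mean the subject's other opioids, as the baseline 24-hour dose recorded at screening suggests.

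**What to change.** In Appendix H, label the existing key *100-mcg bottle* and add a line: *400-mcg bottle: 1 spray in 1 nostril = 400 mcg*. Add a number-of-sprays column, which Sections 4.2.2 and 5.1.11.6 already require. A bottle-strength column is a useful optional addition, because it makes each entry self-sufficient. Also optional is a sentence in the route-of-administration paragraph of Section 8.1 saying that its spray counts refer to the 100-mcg bottle.

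The cost is a one-page form revision with IRB approval and slightly more for the subject to write. Dose levels, visit schedule and analyses stay as they are.
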